### 4.2 Exclusion Criteria

1. Female that is pregnant or breastfeeding, or of childbearing potential but not using medically acceptable birth control during study
2. Current mixed episode assessed by clinician judgment as defined by DSM-5 criteria
3. Current active substance use disorder (as defined by DSM-5) with exception of nicotine and caffeine. Participants may be subject to urine drug screen base on study team clinician judgment.

4. Participation in any clinical trial with an investigational drug or device within the last 3 month or concurrent to study participation
5. History of epilepsy, shrapnel or metal in the head or skull, cardiovascular disease/event, OCD, or autism spectrum disorder
6. Clinically defined major neurological disorder; including, but not limited to, seizure disorder and history of loss of consciousness due to head injury for greater than 10 minutes, or documented evidence of brain injury
7. Active suicidal risk based on investigator's clinical judgment
8. Clinically significant unstable medical condition
9. Other condition judged by investigator that could prevent the participant from completion of the study (such as but not limited to, significant physical disability (e.g., hearing/visual deficits) to perform a neutral memory task and/or neuropsychological test battery)
10. Ferromagnetic metal implant or another contraindication to imaging in a 3 Tesla MRI
11. ECT treatment in the past 3 months
12. Minimum of 6 months since last manic or hypomanic episode as defined by DSM-5 criteria

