## 4. SELECTION AND ENROLLMENT OF PARTICIPANTS

### 4.1 Inclusion Criteria

1. 18+ years of age
2. Bipolar I disorder diagnosis as defined by The Diagnostic and Statistical Manual of Mental Disorders, Fifth Edition (DSM-5)
3. Currently experiencing a Major Depressive Episode with Montgomery-Asberg Depression Rating Scale (MADRS)  $\geq 20$  at screening [Day -5/-14] and baseline [Day 0]
4. On a stable and adequate dose of an anti-manic agent (Lithium with a level of at least 0.6, Depakote with a level of at least 50, or a therapeutic dose of carbamazepine, oxcarbazepine, or a neuroleptic for treatment of mania per clinician judgment) without dose changes for at least 6 weeks prior to the active study time period. Final assessment of appropriateness of participant's pharmacologic regimen is subject to study team clinician judgment.
5. Having failed a therapeutic trial of a first line bipolar depression antidepressant (as specified by the Antidepressant Treatment History Form and updated with new medications approved by the FDA for treatment of bipolar depression) in this current episode. This includes a minimum 4 week trial of one of the following medications (minimum dosage): lithium 900mg daily (or blood level  $\geq 0.6$  mEq/L), carbamazepine 400mg daily (or blood level  $\geq 0.8$  mEq/L), lamotrigine 200mg daily, asenapine 20mg daily, lurasidone 20mg daily, olanzapine 10mg daily, quetiapine 300mg daily, or lumateperone 42mg daily. Final determination of a failed adequate therapeutic trial is subject to study team clinician judgement.
6. Established outpatient psychiatrist

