#### **10.3.3 Monitoring**

Study team will meet to discuss potential participants after screening and record review to ensure they meet inclusion/exclusion criteria and are appropriate for this study. Study team will have monthly meetings to review and ensure protocol compliance as participant's are enrolled and undergo active study treatment.

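### Exclusion criterion 12 is worded as a requirement: taken literally, it bars people six or more months clear of mania or hypomania and does not bar those with a more recent episode

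*Combined protocol and SAP*

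**What the plan says.** Protocol Section 4.2 is the exclusion list and has twelve items. Item 12 reads "Minimum of 6 months since last manic or hypomanic episode as defined by DSM-5 criteria".

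Two other items in the list also concern how recent something is. Item 4 reads "Participation in any clinical trial with an investigational drug or device within the last 3 month or concurrent to study participation" and item 11 reads "ECT treatment in the past 3 months". Both describe a recent exposure that rules a person out.

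Three further criteria touch on mood state or anti-manic treatment. Inclusion 3 (Section 4.1) requires a current major depressive episode with MADRS of at least 20 at screening and baseline. Inclusion 4 requires a stable anti-manic regimen "without dose changes for at least 6 weeks prior to the active study time period". Exclusion 2 covers "Current mixed episode assessed by clinician judgment as defined by DSM-5 criteria". None of the three states how long ago the last manic or hypomanic episode must have been.

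On how the criteria are applied, Section 10.3.3 says: "Study team will meet to discuss potential participants after screening and record review to ensure they meet inclusion/exclusion criteria".

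**The concern.** An exclusion list works by one rule: if the statement is true of a person, that person is out. Item 12 states something the sponsor presumably wants to be true of everyone enrolled, so under that rule its effect is reversed.

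The item matters more here than a stray wording slip would elsewhere. Emergent mania stops a participant's treatment (Sections 5.1, 6.2, 7.1 and 7.2), unresolved hypomania is the only ground for terminating the study in Section 9.2, and the YMRS is a second primary outcome (Section 9.3.1). Item 12 is the only place where the protocol sets a time since mania or hypomania, so its direction should not depend on the reader's inference.

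There is also a compliance problem. If the sites apply the evident intent, each person they enrol meets exclusion 12 on its face. Section 10.3.2 requires study deviations to go to the IRB within 10 days, and the approved text would put the deviation on the wrong participants.

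**Working it through.** No arithmetic is at issue and the plan gives no figure to reproduce. The check is a logical reading of item 12, followed by a search for any other text that settles its direction.

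**Step 1: direction of item 12.** Let T be the months since the last manic or hypomanic episode. The item's statement is true when T ≥ 6.

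| T | Item 12 read literally, as an exclusion | Item 12 read as a requirement |
|---|---|---|
| T ≥ 6 | statement true, person excluded | condition satisfied, not barred |
| T < 6 | statement false, not barred by this item | condition not satisfied, person excluded |

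The two columns disagree in both rows, so there is no value of T at which the readings agree.

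**Step 2: is the wording a convention of the list?** Items 1 to 11 each name a state, history or judgment that removes a person. The closest comparators, items 4 and 11, give a look-back window and exclude people whose exposure falls inside it. Only item 12 gives an interval that must have passed. A rule that reads items 1 to 11 correctly reverses item 12.

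**Step 3: does other text state the interval?**

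- Inclusion 3 fixes the current mood state and is silent on T.
- Inclusion 4 concerns 6 weeks of unchanged anti-manic dosing. That is not a mania-free interval.
- Inclusion 5 requires failure of a drug trial of at least 4 weeks within the current episode. This implies a depressive episode at least about that long, but sets no interval since mania.
- Exclusion 2 covers a current mixed episode, not a past manic or hypomanic one.
- The rest of the protocol, including the synopsis and Sections 3, 6, 7 and 9, states no interval since mania or hypomania.

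**Step 4: what is left open.** Inclusions 3 and 5 together make it hard to enrol someone whose mania ended less than about 4 weeks ago. This assumes that the failed trial ran wholly after the mania. It also depends on clinician judgment, to which inclusion 5 leaves the final determination. The range in which item 12 is the only relevant text therefore runs from roughly one month to six months since the last episode. In that range the literal text does not bar entry and the evident intent does.

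**The case against.** The strongest reply is that nobody would follow the literal text. The word minimum signals a threshold to be reached, and excluding people with bipolar I disorder because they have been free of mania for six months makes no sense in this trial. The protocol also speaks loosely of participants meeting its inclusion and exclusion criteria together (Sections 4.3, 6.2 and 10.3.3), so a reader may take every item as something to satisfy. Eligibility is not decided mechanically either: a trained rater administers the SCID, records are reviewed, and the study team discusses candidates. The other criteria in Step 4 limit entry after very recent mania.

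Most of this stands. The intent is easy to infer, and the literal reading does not open the trial to everyone with recent mania. It does not make the text right. Under the loose usage, items 1 to 11 must be negated and item 12 must not, so the list would run on two opposite conventions without saying so. Team review checks candidates against these same criteria.

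Some stronger inferences are tempting but unsupported:

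- **That the wrong people will be enrolled.** The pre-consent screener mentioned in Section 4.3 is not among the documents and may already run the right way.
- **That those let in are the people most likely to switch.** The documents give no switch risk by time since mania.
- **That the criterion cannot be audited.** It has a stated duration and a DSM-5 definition, so either reading can be checked once the direction is fixed.
- **That one such enrolment is a tenth of the sample of 10, or brings the study towards its three-case stopping rule.** The first is only a ratio. Section 9.2 counts participants with a YMRS score above 10 that does not resolve within 24 hours, and nothing in the documents links past mania to that count.

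**Conclusion.** The point holds as an error of direction in current eligibility text. Item 12 is wrong as written: on this one item it gives the opposite of its evident purpose for every candidate, and no other section corrects it. In practice the effect is bounded by the other criteria to roughly one to six months since the last episode, and by the likelihood that staff apply the intended meaning.

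The conclusion rests on two assumptions: that an item in an exclusion list excludes when it is true, and that the sponsor intended a mania-free interval of at least 6 months. The first is the ordinary meaning of the heading. The second is an inference, though a strong one, and the sponsor should confirm it. Nothing here judges whether 6 months is the right interval.

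**What to change.** Reconcile item 12 with the list it sits in, keeping the sponsor's own 6-month interval and DSM-5 definition. Either route works:

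- leave it in Section 4.2 and phrase it as a reason to exclude, namely a manic or hypomanic episode in the past 6 months; or
- move the existing sentence to Section 4.1 as an inclusion criterion.

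Then confirm that the pre-consent screener and any eligibility checklist at both sites use the same direction. If anyone has already been enrolled, record which reading was applied.

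The cost is a one-line amendment and a check of the forms. If the sites already apply the evident intent, recruitment is unaffected.

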#### **4.3 Study Enrollment Procedures**

At Johns Hopkins University, participants will be recruited through clinics affiliated with the Johns Hopkins Mood Disorders Center in the Department of Psychiatry and Behavioral Sciences, or they may be referred to the study by other Johns Hopkins and community physicians. Clinicians will consider potential patients who meet inclusion/exclusion criteria and discuss the study with them. Then, the clinician or patient may contact the study team to schedule a meeting to undergo the consent and formal screening process. Once a study team member has been contacted, they may send potential participants a pre-consent screener via REDCap survey. This screener focuses on basic questions to establish whether the individual may be eligible to participate in the study. A copy of the screener is included with this application. The screener will explain why we are asking these questions and will inform the individual that their responses are completely voluntary. The screener will also inform the individual that any information we collect on them will be permanently removed if they decide not to participate in the study or are not eligible to participate.

At University of Texas at Austin, participants will be recruited through the UT Health Austin Bipolar Disorder Center. UT Austin and community physicians may also refer patients who may be eligible to participate in this study.

At both sites, the consenting and clinical screening assessment will be preformed in-person in a private office setting, or virtually by secure audio/video platform as works best for the individual and current COVID environment. Only after the consenting process will patient medical records be reviewed as provided by patient or patient's mental health provider.

## 5. STUDY INTERVENTIONS

### 5.1 Interventions, Administration, and Duration

#### **Device Rationale:**

In our study, iTBS will be delivered using the Magnus Transcranial Magnetic Neuromodulation System (MNS). MNS consists of the MagVenture MagPro X100 rTMS Stimulator System (Magventure A/S, Denmark) equipped with a MagVenture Cool-B65 coil. A Localite neuronavigation system (Localite GmbH, Sankt Augustin, Germany) will be used to position the TMS coil over the individualized stimulation target at each session. MagVenture has a 40+ history in the development of safe and reliable TMS stimulators which have widespread clinical and research use. We will follow the dosing that was used successfully in the prior SAINT study carried out by members of our collaborative study team. This is the same equipment that has been used for all published SAINT clinical trials to date.

Traditional 10Hz TMS treatment is on label for the MagVenture MagPro X100 device we are using. Theta burst with an X100 is FDA cleared for treatment of MDD (K173620). No TMS is FDA cleared yet for treating bipolar depression. So, we are using a TMS machine that is FDA-cleared for treating MDD, but for a non-FDA-cleared indication, bipolar depression.

Theta burst stimulation (iTBS) is minimal risk because the risk of seizure is very low (only reported once in literature) and there is no other risk other than minimal scalp irritation. We are using iTBS with “off label” stimulation parameters which have a lower risk profile than the on label approved parameters. Specifically, these parameters include: 1) 1800 pulses of iTBS (600 was in clearance, but only 1800 has been shown to work in a blinded RCT), 2) 10 session per day instead of 1, 3) 90,000 overall pulses instead of 18,000 total, 4) 5 days instead of 36, 5) 90% depth adjusted intensity instead of 120% non-depth adjusted, and neuronavigated targeting. The increased dose and dose density increases the risk, the lower stimulation intensity, fewer days, and navigated targeting all reduce risk.

#### **Treatment Details:**

Motor threshold: Using single pulse TMS, the scalp position of lowest motor threshold for the left first dorsal interosseous or abductor pollicis brevis muscles will be determined. Resting motor threshold (MT) will be defined by the lowest power setting producing a visible muscle contraction in  $\geq 5$  of 10 trials.

rTMS system and treatment: For this study, we will be using the the MagVenture MagPro X100 rTMS Stimulator System (Magventure A/S, Denmark) equipped with a double-sided MagVenture Cool-B65 coil. A Localite neuronavigation system (Localite GmbH, Sankt Augustin, Germany) will be used to position the TMS coil over the individualized stimulation target at each session. All participants will receive stimulation using iTBS over the LDLPFC (1800 pulses per session). The individualized treatment targets will be produced from structural and functional MRI scans using the software services of Magnus Medical. The targeting approach will be the same as that used in prior publications (Cole et al., 2020, 2022; Williams et al., 2018).

Stimulation intensity will be standardized at 90% of left RMT, adjusted to skull to cortex distance. No further adjustments are needed based on other patient characteristics or conditions. For safety, stimulation will never be delivered above 120% rMT. Sessions will be delivered using the MagVenture MagPro X100 stimulator, with triple-pulse 50-Hz bursts given every 200ms (at 5 Hz).

The iTBS protocol will consist of a 2s train of bursts given every 10 s for a total of 570s (1800 pulses) over the LDLPFC.

If treatment emergent mania occurs (defined as an increase of 2 or more points in at least 2 YMRS items or clinician judgment), we will discontinue treatment and adjust anti-manic medication and, if necessary, add on other pharmacologic measures (neuroleptics, benzodiazepines) as clinically indicated with the intent to treat until remission is achieved.

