### **10.3 Quality Assurance**

#### **10.3.1 Training**

Clinical study staff will undergo or have already undergone training requisite for administration of TMS as well as study clinical measures by

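### Section 5.1 measures motor threshold on a left-hand muscle but treats the left prefrontal cortex, and does not say whether the left RMT used for dosing means hand or hemisphere

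*Combined protocol and SAP*

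**What the plan says.** Everything operative is in section 5.1 of the combined protocol and SAP, under Treatment Details.

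- **Muscle.** Using single-pulse TMS, "the scalp position of lowest motor threshold for the left first dorsal interosseous or abductor pollicis brevis muscles will be determined".
- **Threshold criterion.** "Resting motor threshold (MT) will be defined by the lowest power setting producing a visible muscle contraction" in at least 5 of 10 trials. No side is given here, and the abbreviation is MT.
- **Target.** Every participant is stimulated over the left DLPFC, with 1800 pulses per session.
- **Dose.** "Stimulation intensity will be standardized at 90% of left RMT, adjusted to skull to cortex distance". The abbreviation is now RMT, with *left* attached.
- **Cap.** "For safety, stimulation will never be delivered above 120% rMT". The abbreviation is now rMT, again with no side.

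Two other places bear on the point without settling it. Device Rationale, also in 5.1, says "We will follow the dosing that was used successfully in the prior SAINT study carried out by members of our collaborative study team", but does not report which hand or hemisphere that study used. Section 10.3.1 provides for "training requisite for administration of TMS as well as study clinical measures", but gives no threshold procedure.

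**The concern.** The hand muscles are controlled by the opposite motor cortex. That is basic anatomy rather than something the protocol states. A threshold taken on a left-hand muscle therefore describes the right hemisphere, whereas the treatment is applied to the left.

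The 90% dose and the 120% cap are both percentages of the threshold, and the protocol describes only one way of measuring it. Device Rationale concedes that the larger pulse dose and dose density raise risk. Among the offsets it lists "90% depth adjusted intensity instead of 120% non-depth adjusted, and neuronavigated targeting". The meaning of that 90% depends on whose threshold it refers to. The pilot is also meant to lead to a larger multisite study, so an unclear dosing rule could be carried forward.

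**Working it through.** The plan gives no figure to reproduce. The check is first a comparison of the statements, then an illustration of sensitivity.

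**1. The two readings of *left RMT*.**

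- *Left means left hand.* The measurement and dosing sentences then agree with each other. The dose and cap are percentages of the right hemisphere's threshold while the left is treated, and no reason is given.
- *Left means left hemisphere.* The dosing sentence then fits the treated side, but the written procedure never measures that threshold, because the muscle named is on the left hand.

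Either way one sentence needs an edit or an explanation. There is also a smaller ambiguity. Grammatically, *left* may govern both muscles or only the first dorsal interosseous, which would leave the side of the abductor pollicis brevis unstated.

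**2. Does any other text resolve it?** Motor threshold is discussed only in section 5.1. The skull-to-cortex adjustment corrects for distance, not for the hemisphere measured. The training provision (10.3.1) and the monthly protocol-compliance meetings (10.3.3) name no side.

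**3. Sensitivity under the literal reading.** Let L and R be the left- and right-hemisphere thresholds, with R = L × (1 ± d). The value of d is an assumption, because the documents give no side-to-side difference. Depth adjustment is left out because its form is not given.

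- Nominal dose as a percentage of the treated side's threshold = 90 × (1 ± d)
- Cap on the same scale = 120 × (1 ± d)

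| Assumed d | Nominal 90% becomes | 120% cap sits at |
|---|---|---|
| 0 | 90% | 120% |
| 5% | 85.5% to 94.5% | 114% to 126% |
| 10% | 81% to 99% | 108% to 132% |
| 15% | 76.5% to 103.5% | 102% to 138% |

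The nominal dose equals 100% of the treated side's threshold when R/L = 100/90 = 1.111. It equals 120% only when R/L = 120/90 = 1.333. The cap column shows where the limit would lie, not a dose shown to be reached.

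**The case against.** The best case for the plan is that this may be a one-word drafting slip. Trained operators would place the coil as in the earlier SAINT work, whose dosing the protocol adopts. Read in sequence, *left RMT* is simply the threshold just measured on the left-hand muscle, so the section can be read as self-consistent. Training and monthly compliance meetings make an unnoticed error less likely.

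Much of that stands as to practical risk. It does not supply the missing side, and the self-consistent reading is the one that scales the dose to the untreated hemisphere.

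Three stronger readings are tempting, and the documents do not support them.

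- *RMT is undefined.* It is defined: a contraction criterion is given directly after the muscle is named. Only the side is missing, and the abbreviations are inconsistent.
- *The two sites will dose differently.* Nothing in the protocol suggests that they read the text differently. If both follow it literally, both test the left hand and the site difference disappears.
- *Participants will be overdosed, or the risk argument fails.* The percentages in the working rest on assumed differences and precede depth adjustment, so none is a delivered dose. Every nominal dose in the table stays below the 120% non-depth-adjusted comparator in Device Rationale, so the direction of the lower-intensity argument is unchanged.

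**Conclusion.** The point holds as a minor defect in the dosing specification. The mismatch between a left-hand threshold and a left-hemisphere target is clear in the text, and no other section resolves it. Its consequence is not known: it is zero with equal thresholds, and the percentages above are only as good as the assumed d.

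Which side was intended is also not established. The right hand is the natural correction because it corresponds to the treated hemisphere, but the SAINT procedure that the protocol adopts is not reproduced in it. The finding concerns dose clarity and reproducibility. It does not affect the sample size of 10, the endpoints or the analysis model.

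**What to change.** In section 5.1, Treatment Details:

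1. Check the threshold procedure of the prior SAINT study that Device Rationale adopts.
2. Unless that procedure used the left hand, change the muscle to the abductor pollicis brevis or first dorsal interosseous of the **right** hand (left motor cortex, the treated hemisphere), with the side stated for both muscles.
3. If it did use the left hand, say so, give the reason, and define the dosing threshold explicitly as the left-hand, right-hemisphere value.
4. Use one abbreviation, with hand and hemisphere stated once, for the threshold definition, the 90% depth-adjusted dose and the 120% cap.

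The cost is a protocol text amendment: one word for the side and a one-line definition, or a sentence more if the left hand is kept. It adds no procedure, staff time or participants.

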### **Active Study [Day 1-5]:**

TMS sessions will be scheduled in a 5-day sequence, resulting in a total of up to 50 sessions. Prior to each daily treatment series, participants will be asked a short series of

questions assessing medication compliance and substance use, amount and quality of sleep, and any other changes in mood since their last treatment session. We will monitor any medication changes throughout the course of the entire study. Participants will receive up to 10 daily stimulations with active iTBS over the left dorsolateral prefrontal cortex (LDLPFC) (1800 pulses). In the event of depression treatment remission (i.e. MADRS  $\leq 10$ ), treatment emergent mania occurring (defined as an increase of 2 or more points in at least 2 YMRS items), or clinician judgment, LDLPFC treatment will be discontinued and emergent symptoms will be treated by increasing the dose of the participant's anti-manic agent and other pharmacologic measures if necessary as assessed by the onsite clinician.

If participants do not experience a significant increase in manic/hypomanic symptoms ( $\geq 2$  item increase of 2 or more points on the YMRS scale), LDLPFC treatment will continue until MADRS  $\leq 10$  or the end of the 5-day treatment series is reached.

Each session will be separated by a 50-minute break. This separation between stimulation sessions decreases the risk of associated TMS side effects (e.g. irritation from the device, headache). The modified PANAS (items 3, 9, 11, 17, 18, 19) will be administered between every stimulation session to assess for any potential shift towards (hypo)mania. If a significant increase ( $\geq 2$  item increase of 2 or more points) is observed, the YMRS will be administered.

Active study clinical measures collected at beginning and end of each treatment day (unless where noted) will include:

1. YMRS (AM and PM)
2. MADRS (AM, PM, and as clinically indicated)
3. Daily Check-In Form (AM only)

Active study self-report measures collected at end of each treatment day will include:

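### Do the printed train interval, session length and pulse count in Section 5.1 fail to agree, so that the stimulation specification needs correcting?

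*Combined protocol and SAP*

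**What the plan says.** Section 5.1 of the combined protocol and SAP, under Treatment Details, builds the session from three elements. The burst pattern is "triple-pulse 50-Hz bursts given every 200ms (at 5 Hz"). The train pattern, session length and count are a "2s train of bursts given every 10 s for a total of 570s (1800 pulses"). The dose per session is also stated separately: "All participants will receive stimulation using iTBS over the LDLPFC (1800 pulses per session").

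The same count appears elsewhere. The Device Rationale in Section 5.1 gives 1800 pulses per session and a course total of "90,000 overall pulses". Section 6.2 (Active Study) provides for "up to 10 daily stimulations with active iTBS over the left dorsolateral prefrontal cortex (LDLPFC) (1800 pulses") over five days, "resulting in a total of up to 50 sessions". The Device Rationale also points to an earlier trial for the dosing: "We will follow the dosing that was used successfully in the prior SAINT study".

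No other section gives a train interval or a session length. Other timing is given: Section 6.2 puts a 50-minute break between sessions, and Section 3 allows 10 hours for each treatment visit.

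**The concern.** A reader who multiplies out the printed figures does not get 1800. Accelerated iTBS is the only intervention in the study, it is delivered at two sites, and the protocol itself calls its stimulation parameters off label. If one site ended sessions by the clock and the other by the pulse counter, and the interval were exactly 10 s, participants would receive different numbers of pulses under one protocol. Over a full course the time-based reading would give 85,500 to 87,000 pulses against the stated 90,000. The protocol's abstract says the pilot should lead to a larger multisite study, so an unclear specification could also be carried forward.

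**Working it through.** **Inputs.** All are from Section 5.1, Treatment Details, unless noted: 3 pulses per burst; one burst every 0.2 s; 2-s trains; trains every 10 s; 570 s in total; 1800 pulses per session; up to 50 sessions (Section 6.2); 90,000 pulses overall (Section 5.1, Device Rationale).

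**1. Course total.** 50 × 1800 = 90,000. The plan's own total is reproduced exactly.

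**2. Trains needed.** Bursts per train = 2 / 0.2 = 10. Pulses per train = 10 × 3 = 30. Trains for 1800 pulses = 1800 / 30 = 60.

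**3. Trains that fit if 10 s and 570 s are both exact.**

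| Counting rule | Trains | Pulses | Below 1800 |
|---|---|---|---|
| Whole 10-s cycles, 570 / 10 | 57 | 1710 | 90 (5.0%) |
| Last train finished by 570 s (starts at 0, 10, …, 560) | 57 | 1710 | 90 (5.0%) |
| A train starting at 570 s also counted | 58 | 1740 | 60 (3.3%) |

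Reading the 10 s as a rest between trains (a 12-s cycle) moves further away: 48 trains, 48 × 30 = 1440 pulses. No counting rule gives 1800 from exact figures. Over 50 sessions the literal range is 50 × 1710 = 85,500 to 50 × 1740 = 87,000.

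**4. Session length if the interval is exactly 10 s and 60 trains are given.** The last train ends at 59 × 10 + 2 = 592 s, or 60 × 10 = 600 s with the final rest. That is 22 to 30 s more than printed.

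**5. Interval that fits 60 trains into exactly 570 s.**

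- Whole cycles: 570 / 60 = 9.50 s.
- Last train ends at 570 s: (570 − 2) / 59 = 9.63 s.
- Last train starts at 570 s: 570 / 59 = 9.66 s.

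All three print as 10 s to the nearest second (9.50 s with halves rounded up). If 570 s is itself rounded to the nearest 10 s, which is an assumption, the upper limit for a last train that ends in time becomes (575 − 2) / 59 = 9.71 s. The printed figures are therefore compatible at the precision used.

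**6. Effect on the treatment day.** Ten 570-s sessions with nine 50-minute breaks take 95 + 450 = 545 minutes, about 9.1 hours. Ten 600-s sessions take 100 + 450 = 550 minutes, about 9.2 hours. Both fit the 10-hour visit in Section 3, so the schedule neither settles the question nor is disturbed by it.

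**7. Effect on the statistics.** Section 9.1 bases the sample size on feasibility and resources. In Section 9.4 the clinical models adjust for age, sex and days to remission, and the connectivity analysis uses sex and site. Pulse count and session length enter none of these.

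**The case for a change.** The best case for a change is that the rounding is inferred, because no section says the interval is approximate. With 570 s held exact, only about 9.50 to 9.66 s works, which is the lowest 13 to 16% of the range that would print as 10 s (9.5 to 10.5 s). The documents also do not show which figure is approximate: an exact 10-s interval with a session of 592 to 600 s would give 1800 pulses too. Nor does the text say whether time or count ends a session. The reference to an earlier trial puts the settling detail outside the protocol, which ought to be readable on its own, and the cure would be one sentence.

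Much of this stands. The sentence is looser than it should be, and which figure is approximate cannot be decided from the documents. What does not follow is a consequence for the trial. The step from a loose interval to fewer pulses requires someone to set aside a count that the protocol assigns to every participant in every session and confirms through the course total. Nothing in the documents suggests that either site would do so. The two readings that keep the 1800 count differ by 22 to 30 s in session length and not at all in pulses.

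**Conclusion.** No change to the plan follows. Taken as exact, the interval and duration give 1710 to 1740 pulses, 3.3 to 5.0% below the stated 1800. Taken as whole-second figures, they agree with it. The remaining point is an unstated rounding in one sentence, which is a clerical matter. The pulse count is consistent wherever it appears and reproduces the 90,000 total, and the sample size rationale, the models and the visit schedule are unaffected.

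This rests on two conditions: that sessions deliver the stated count, as the protocol says for all participants, and that at least one of the two timing figures is rounded, which the documents allow but do not state. Which figure is approximate is for the investigators to say, and they can reconcile the three values if the section is edited for another reason. No view is taken here on which stimulation setting is right.
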